3.1.2 Efmarodocokin Alfa Administration

Patients enrolled in the extension study will receive efmarodocokin alfa treatment or undergo observation for up to approximately 2 years (through Week 104), as determined on the basis of the patient's disease status, as outlined in [Table 2](#). Upon entry into the extension study, patients will receive efmarodocokin alfa 60 µg/kg IV Q4W or undergo observation, depending on their disease status at the time of their last endoscopy in the parent study. The first dose of efmarodocokin alfa in the extension study may not be administered less than 2 weeks after last dose of study drug in parent study. During the extension study, patients will receive efmarodocokin alfa 60 µg/kg IV Q4W or undergo observation, depending on their disease status at a scheduled visit or a disease evaluation visit (details on disease evaluation visits are provided in [Section 3.1.5](#)).

Table 2 Efmardocokin Alfa Treatment Algorithm

Patient's Disease Status	Action to Be Taken
Meets criteria for clinical remission ^a	
Discontinue efmardocokin alfa (if applicable)Undergo observation and assessments per schedule of activities (see Appendix 1)
Does not meet criteria for clinical remission ^a	
Receive efmardocokin alfa 60 µg/kg IV Q4W until clinical remission is achieved ^bUndergo assessments per schedule of activities (see Appendix 1)
Meets criteria for disease flare ^c (off treatment) after entry into study	
Consult with Medical Monitor to determine appropriate course of action prior to administration of efmardocokin alfa (if applicable)
Experiences disease worsening as a result of efmardocokin alfa treatment, in the investigator's judgment, or disease flare while receiving efmardocokin alfa ^c	
Permanently discontinue efmardocokin alfaInitiate rescue therapy at discretion of investigatorUndergo safety follow-up assessments 8 weeks after final dose of efmardocokin alfa ^d

Q4W=every 4 weeks.

^a Clinical remission during the extension study, as defined in Section [3.1.4.3](#).

^b First dose of efmardocokin alfa in the extension study to be administered no less than 2 weeks after last dose of study drug in parent study

^c Disease flare during the extension study, as defined in Section [3.1.4.4](#).

^d See Section [3.1.6](#) and [Appendix 1](#) for details regarding safety follow-up.

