3.1.6 Safety Follow-Up Visit and Early Termination Visit

Patients will undergo safety follow-up or early termination assessments as outlined below:

- Patients who receive at least one dose of efmarodocokin alfa must undergo safety follow-up assessments 8 weeks after their final dose of study drug.

Patients who discontinue the study prematurely (prior to Week 104) and have received at least one dose of efmarodocokin alfa should return to the clinic for an early termination visit within 1 week. Patients who discontinue prematurely without having undergone at least 8 weeks of follow-up (observation) after their final dose of efmarodocokin alfa should also return to the clinic for a safety follow-up visit 8 weeks after their final dose.

Patients who are unwilling to complete the safety follow-up visit should return to the clinic for an early termination visit no later than 30 days after their final dose.

- Patients who discontinue the study prematurely (prior to Week 104) and have not received efmarodocokin alfa should return to the clinic for an early termination visit within 30 days. Follow-up assessments are not required for patients who discontinue the study at Week 104 without having received efmarodocokin alfa.

For patients who complete Week 52 and safety follow-up assessments prior to the implementation of Protocol Version 6 and re-enter the study, safety follow-up is to be repeated for Year 2, as outlined above. Details regarding assessments at the safety follow-up visit and the early termination visit are provided in [Appendix 1](#).

Patients who permanently discontinue study drug can receive rescue therapy at the investigator's discretion.

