4.5.5.6 Endoscopy with Biopsies

All patients will undergo an endoscopy, consisting of a flexible sigmoidoscopy for patients with UC and an ileocolonoscopy for patients with CD, with collection of biopsies at specified timepoints during the study and at the disease evaluation/early termination visit. Endoscopy at the early termination visit should be conducted if the investigator deems it necessary. All patients will undergo annual endoscopies for colon cancer surveillance. The endoscopies should include the following:

- Removal of any adenomatous polyps
- Performance of multiple random mucosal biopsies to evaluate for dysplasia

Annual dysplasia surveillance should be performed according to local guidelines, taking into consideration endoscopic technique as well as the appropriateness of performing surveillance for dysplasia in the presence of active inflammation. Surveillance may be delayed per local guidelines (i.e., if there is extensive active inflammation) to enable more accurate pathologic diagnosis.

Every effort should be made to schedule on-treatment endoscopies on the same day as the protocol-specified study visit.

Bowel preparation prior to the endoscopy should be done per local practice. Medications used for bowel preparation should be reported on the Concomitant Medications eCRF. Scheduled stool samples should be taken prior to bowel preparation.

For each patient, a video recording will be performed during the endoscopy through use of a medical DVD recorder in the high-quality mode per the endoscopy manual. Video recordings should be taken of the entire endoscopic procedure, starting from insertion into the bowel. Biopsies should be performed upon withdrawal of the endoscope from the bowel. The endoscopist should ensure that the video recording of the procedure will allow for adequate assessment of disease activity, taking into consideration the possibility of minor bleeding associated with biopsies. Technical instructions for video recording and biopsy collection are provided in the laboratory manual.

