5.1.1.3 Epithelial Tumor Promotion

IL-22 has been reported to promote epithelial tumor progression, including squamous cell and basal cell carcinoma (Nardinocchi et al. 2015) and colorectal cancer (Kirchberger et al. 2013; Kryczek et al. 2014). There has been no evidence of epithelial tumor promotion in the Phase Ia study (GA29468), the Phase Ib study (GA29469), or nonclinical studies to date. Nevertheless, given the a priori elevated risk of malignancy in this patient population, and the potential for epithelial tumor promotion with IL-22 in tumor cells that may express the IL-22 receptor (refer to the Efmarodocokin Alfa Investigator's Brochure), the trial includes selection criteria and additional safety monitoring to minimize any hypothetical risk.

Patients with any history of cancer were excluded from Study GA29469. Patients with a history of cancer within the past 5 years and patients with a history of non-melanoma skin cancer or GI and/or colon cancer, or a known family history of GI and/or colon cancer (defined as one first-degree relative or two second-degree relatives) were excluded from Study GA39925. In addition, patients with a history of CIN of Grade >1,

cervical smear indicating the presence of AIS or HSILs, and patients who had evidence of unresectable colonic mucosal dysplasia or high-grade colonic mucosal dysplasia were excluded from Study GA39925. Patients in both parent studies had to have documentation of colon cancer surveillance within 1 year prior to enrollment.

Guidelines for management of patients who develop epithelial tumor promotion are provided in Section 5.1.2.3.

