5.3.1 Adverse Event Reporting Period

Investigators will seek information on adverse events at each patient contact. All adverse events, whether reported by the patient or noted by study personnel, will be recorded in the patient's medical record and on the Adverse Event eCRF.

After informed consent for study entry has been obtained but prior to initiation of study drug, only serious adverse events caused by a protocol-mandated intervention (e.g., invasive procedures such as biopsies, discontinuation of medications) should be reported (see Section 5.4.2 for instructions for reporting serious adverse events).

After informed consent for study re-entry has been obtained (see Section 3.1.3) but prior to initiation of study drug, only serious adverse events caused by a protocol-mandated intervention (e.g., invasive procedures such as biopsies, discontinuation of medications) or prior study treatment should be reported (see Section 5.4.2 for instructions for reporting serious adverse events).

After initiation of study drug following study entry or study re-entry, all adverse events will be reported until 8 weeks after the final dose of study drug.

Any adverse event that occurs after completion of Week 52 and required safety follow-up assessments but prior to obtaining informed consent for study re-entry should be captured on the General Medical History and Baseline Conditions eCRF rather than the Adverse Event eCRF, unless it is a serious adverse event related to prior study treatment.

Instructions for reporting adverse events that occur after the adverse event reporting period are provided in Section 5.6.

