5.6 ADVERSE EVENTS THAT OCCUR AFTER THE ADVERSE EVENT REPORTING PERIOD

The Sponsor should be notified if the investigator becomes aware of any serious adverse event that occurs after the end of the adverse event reporting period (defined as 8 weeks after the final dose of study drug), if the event is believed to be related to prior study drug treatment. These events should be reported through use of the Adverse Event eCRF. However, if the EDC system is not available, the investigator should report these events directly to the Sponsor or its designee, by faxing the paper Clinical Trial Serious Adverse Event/Adverse Event of Special Interest Reporting Form using the fax number provided to investigators.

5.7 EXPEDITED REPORTING TO HEALTH AUTHORITIES, INVESTIGATORS, INSTITUTIONAL REVIEW BOARDS, AND ETHICS COMMITTEES

The Sponsor will promptly evaluate all serious adverse events and adverse events of special interest against cumulative product experience to identify and expeditiously communicate possible new safety findings to investigators, IRBs, ECs, and applicable health authorities based on applicable legislation.

To determine reporting requirements for single adverse event cases, the Sponsor will assess the expectedness of these events *through the use of the reference safety information in the document listed below:*

Drug	Document
Efmarodocokin alfa	Efmarodocokin Alfa Investigator's Brochure

The Sponsor will compare the severity of each event and the cumulative event frequency reported for the study with the severity and frequency reported in the applicable reference document.

Reporting requirements will also be based on the investigator's assessment of causality and seriousness, with allowance for upgrading by the Sponsor as needed.

Currently there are no expected serious adverse drug reactions for efmarodocokin alfa described in the Efmarodocokin Alfa Investigator's Brochure. Thus, any treatment-emergent serious adverse event deemed related to efmarodocokin alfa will be reported as a suspected unexpected serious adverse reaction (SUSAR). Reporting of individual SUSARs to investigators, IRBs, ECs, and applicable health authorities will be done in accordance with applicable legislation.

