- ^d Treatment initiation (i.e., first visit of period in which patient receives efmarodocokin alfa) may coincide with the Study Week 0 (baseline) visit or a subsequent scheduled visit that confirms the patient is not in clinical remission. The first dose of efmarodocokin alfa in the extension study is to be administered no less than 2 weeks after the last dose of study drug in parent study. For patients who complete the Week 52 visit but have not yet completed required safety assessments prior to the implementation of Protocol Version 6 (see Section 3.1.3): If treatment is resumed (*follow “Q4W When Not in Clinical Remission” column*), there must be a minimum of 2 weeks since the last dose of efmarodocokin alfa. For patients who complete the Week 52 visit and (if required) safety follow-up assessments prior to the implementation of Protocol Version 6: If the patient qualifies for study re-entry and is not in clinical remission, efmarodocokin alfa must be given within 1 week of establishing eligibility (*follow “Q4W When Not in Clinical Remission” column*).
- ^e For patients who achieve clinical remission while receiving efmarodocokin alfa, Q8W visits begin 16 weeks after *achieving clinical remission*.
- ^f Additional activities to be performed in all patients.
- ^g Patients with worsening disease, as determined by the investigator, should return to the clinic as soon as possible for a disease evaluation visit. The investigator may also schedule a disease evaluation visit to determine if a patient has achieved clinical remission. Patients who discontinue study drug prematurely (prior to Week 104) for the reasons listed in Section 4.6.1 and have received at least one dose of efmarodocokin alfa should return to the clinic for an early termination visit within 1 week of the event and will then enter the safety follow-up period. Patients who are unwilling to complete the safety follow-up period should return to the clinic for an early termination visit no later than 30 days after their final dose. Patients who discontinue the study prematurely (prior to Week 104) and have not received efmarodocokin alfa should return to the clinic for an early termination visit within 30 days. Endoscopy at the early termination visit should be conducted if the investigator deems it necessary.

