- ¹ After informed consent for study entry has been obtained but prior to initiation of study drug, only serious adverse events caused by a protocol-mandated intervention should be reported. After informed consent for study re-entry has been obtained (see Section 3.1.3) but prior to initiation of study drug, only serious adverse events caused by a protocol-mandated intervention (e.g., invasive procedures such as biopsies, discontinuation of medications) or prior study treatment should be reported. After initiation of study drug following study entry or study re-entry, all adverse events will be reported until 8 weeks after the final dose of study drug. After this period, the Sponsor should be notified if the investigator becomes aware of any serious adverse event that is believed to be related to prior study drug treatment (see Section 5.6). Any adverse event that occurs after completion of Week 52 and required safety follow-up assessments but prior to obtaining informed consent for study re-entry should be captured on the General Medical History and Baseline Conditions eCRF rather than the Adverse Event eCRF, unless it is a serious adverse event related to prior study treatment.
- ^m Vital signs include measurements of respiratory rate, pulse rate, systolic blood pressure, diastolic blood pressure, and temperature. Patient should be in a seated position after at least 10 minutes of rest prior to measuring vital signs.
- ⁿ A complete physical examination includes evaluation of the head, eyes, ears, nose, and throat, and the cardiovascular, dermatologic, musculoskeletal, respiratory, gastrointestinal, genitourinary, and neurologic systems. Record abnormalities observed at baseline (Study Week 0) on the General Medical History and Baseline Conditions eCRF.
- ^o Perform a limited, symptom-directed examination, including an abdominal examination, at specified timepoints or as clinically indicated. Record new or worsened clinically significant abnormalities on the Adverse Event eCRF.
- ^p Patient must be resting in a supine position for at least 10 minutes prior to ECG assessment. ECGs are to be obtained prior to other procedures scheduled at that same time (e.g., vital sign measurements, blood draws) and should not be obtained within 3 hours after any meal if possible. ECGs should be performed at each dosing visit until after the shortest tolerated infusion delivery time is reached (i.e., infusion is tolerated without infusion-associated adverse event).

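### Adverse-event reporting closes 8 weeks after the final dose although off-drug observation runs to Week 104, so late non-serious dysplasia and serious events judged unrelated are likely under-recorded

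*Combined protocol and SAP*

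**What the plan says.** Section 5.3.1 sets the rule: after study drug starts, "all adverse events will be reported until 8 weeks after the final dose of study drug". Section 5.4.2.2 puts the same limit on serious adverse events (SAEs) and adverse events of special interest (AESIs). Beyond it, Section 5.6 asks for notification of a serious event only "if the event is believed to be related to prior study drug treatment". Appendix 1 footnote l attaches the restriction to the adverse-events row of the schedule: "After this period, the Sponsor should be notified if the investigator becomes aware of any serious adverse event that is believed to be related". Section 5.3.5.9 sends later deaths to Section 5.6 as well.

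Follow-up does not stop with the drug. Under Table 2 (Section 3.1.2) a patient in remission discontinues efmarodocokin alfa and is to "Undergo observation and assessments per schedule of activities", through Week 104. Endoscopy is scheduled at Weeks 28, 52, 80 and 104, and Section 4.5.5.6 adds: "All patients will undergo annual endoscopies for colon cancer surveillance". Footnote e reads: "For patients who achieve clinical remission while receiving efmarodocokin alfa, Q8W visits begin 16 weeks after" remission. For a patient who remits on drug and is not restarted, every such visit therefore falls after the reporting window.

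Section 5.1.1.3 lists epithelial tumor promotion as a risk and justifies extra monitoring "given the a priori elevated risk of malignancy in this patient population". Neoplasia is not itself an AESI in Section 5.2.3. The AESI for events that lead to stopping study drug cannot apply to a patient already off it.

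**The concern.** Long-term safety is the study's main purpose, and Section 6.4 names the impact of intermittent dosing as something to be evaluated. Off-drug time is what defines a treat-to-remission strategy. In that time the plan keeps looking for neoplasia by endoscopy and biopsy, but the reporting rule no longer takes in everything that is found. Two kinds of finding are exposed: dysplasia not classed as serious, and serious events, including cancers and deaths, that the investigator attributes to something else. The elevated background risk acknowledged in Section 5.1.1.3 makes the second likely, because Table 6 accepts underlying disease as evidence against relatedness.

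**Working it through.** **Inputs.** Dosing is every 4 weeks until remission (Table 2), with the first dose at Week 0 for patients not in remission (Appendix 1 footnote c). Reporting runs to 8 weeks after the final dose (5.3.1). Follow-up is 104 weeks (3.1.2). Section 6.1 assumes 135 evaluable patients, 20% in sustained remission, and 52-week SAE rates of 6.6% or 13.5%. Assumptions added here: one uninterrupted course, no restart, full follow-up.

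**The plan's own figures.** Section 6.1 states no quantity for this point, but its intervals give a yardstick. For 20%, the Wald interval 0.20 ± 1.96 × √(0.20 × 0.80/135) is 13.3% to 26.7%, as stated. For SAEs, exact intervals for 9/135 and 18/135 are 3.1% to 12.3% and 8.1% to 20.3%, matching the stated 3% to 12% and 8% to 20%.

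**Time outside the window.** With k infusions the last dose is at Week 4(k − 1), the window closes at Week c = 4(k − 1) + 8, and the weeks outside are 104 − c (not below 0).

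| Infusions | Last dose (Week) | Window closes (Week) | Weeks outside | Share of 104 | Scheduled endoscopies outside |
|---|---|---|---|---|---|
| 3 | 8 | 16 | 88 | 85% | 4 of 4 |
| 7 | 24 | 32 | 72 | 69% | 3 of 4 |
| 13 | 48 | 56 | 48 | 46% | 2 of 4 |
| 26 | 100 | 108 | 0 | 0% | 0 of 4 |

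**Scale across the study.** If the assumed 20% (27 of 135) all remit after 7 infusions and stay off drug, 27 × 72/52 = 37.4 of 135 × 2 = 270 patient-years (14%) lie outside the window. The timing of remission is an assumption. With 3 or 13 infusions instead, the figure is 45.7 (17%) or 24.9 (9%).

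**How much of that time is blind.** Let r be the share of late events still reported because they are serious and believed related. The follow-up effectively uncovered is (1 − r)(104 − c)/104. After 7 infusions this is 69% for r = 0, 35% for r = 0.5 and 0% for r = 1. The documents do not give r. For non-serious findings, Section 5.6 sets it to 0.

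**Overall 52-week SAE rate, worst case (r = 0).** At a constant hazard, the recorded risk to Week 32 is 1 − (1 − p)^(32/52), which is 4.11% for p = 6.6% and 8.54% for p = 13.5%. If 20% of patients close at Week 32, the pooled rates become 0.8 × 6.6 + 0.2 × 4.11 = 6.1% and 0.8 × 13.5 + 0.2 × 8.54 = 12.5%. Both lie well inside the planned intervals.

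**The case against.** **Other reporting routes exist.** Section 5.3.1 has adverse events sought at every contact and noted in the medical record, and Appendix 1 marks them at off-drug visits. Section 5.1.2.3 (Epithelial Tumors) asks that clinical findings pointing to cancer be reported to the Sponsor, without a time limit or causality test. It also lets the Sponsor request tissue once cancer or high-grade dysplasia is diagnosed. Table 6 makes related the default. A reader might infer that late neoplasia reaches the Sponsor only if serious and believed related; these provisions show that this goes too far. They do not close the gap. Footnote l restricts the Appendix 1 row itself, and Section 5.1.2.3 names no Adverse Event eCRF entry after the window and does not clearly cover low-grade dysplasia found only on biopsy.

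**A dose trend does not follow.** A reader might infer that low-infusion groups in Section 6.4 would be undercounted and that neoplasia would seem to rise with number of infusions. The documents do not support that. Section 6.4 sets no cut-points. Patients who stop early and leave after safety follow-up also have few infusions, and no surveillance is discarded for them. Above all, Section 4.6.1 and Table 4 require permanent discontinuation for malignancy, high-grade or unresectable colonic dysplasia and cervical intraepithelial neoplasia above Grade 1. Such a diagnosis ends dosing, so final infusion count depends on the outcome. Grade 4 events that stop drug raise the same problem for SAEs.

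**Final dose may be open.** A patient who may yet be retreated after a flare has arguably not had a final dose, and a restart reopens reporting. Section 3.1.6 does speak of patients "without having undergone at least 8 weeks of follow-up (observation) after their final dose of efmarodocokin alfa", but those patients are leaving the study, so the final dose is then known. This objection stands in part: sites could read the term differently, which is itself a reason to clarify it.

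**Later recovery is possible.** Medical records and endoscopy videos remain, so late events are not irretrievable. Recovering them would take a site query.

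**Conclusion.** The concern holds for one defined group: dosed patients in sustained off-drug remission who remain in the study. Applied as written, the reporting rules are likely to under-record their non-serious dysplasia and their serious events judged unrelated. The uncovered time is large for an early remitter (69% of 104 weeks after 7 infusions) and zero for a patient dosed to Week 100, given one uninterrupted course and no restart. The number of events lost cannot be derived: the documents give neither a neoplasia rate nor the share of late events that would be judged serious and related. The overall 52-week SAE rate would move little, from 6.6% to 6.1% or from 13.5% to 12.5% under the worst-case assumption shown. The analyses are descriptive, and no stated sample size or interval changes. This is a cheap improvement to safety ascertainment, not a flaw that overturns the analysis.

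**What to change.** In Sections 5.3.1, 5.4.2.2 and 5.6 and Appendix 1 footnote l: for dosed patients still in the study, record on the Adverse Event eCRF any malignancy, any colonic dysplasia and all SAEs, regardless of causality, until the later of 8 weeks after the final dose and the last study visit. Keep the 8-week rule for other non-serious events. This also gives the malignancy instruction in Section 5.1.2.3 a defined recording route and removes the dependence on how a site reads final dose.

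In Section 6.4, report these events per person-time, split into on drug (to 8 weeks after a dose) and off drug. Count cumulative exposure up to the event, not by final infusion group, because the latter can be determined by the event.

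Cost: no new visit or procedure, since the off-drug visits and endoscopies are already scheduled. The downside is more SAE reports from off-drug time, many of them background, which the on-drug/off-drug split keeps apart. Off-drug time that has already elapsed would need a retrospective query to sites.
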